The main treatment approaches for chronic insomnia with proven efficacy are pharmacologic and behavioral treatment. In accordance with the results of multiple clinical trials and meta-analyses both methods have comparable effectiveness in terms of sleep quality ranging between 64% (Buysse et.al., 2011) and 88% (Carson, McDonagh, Thakurta, and Yen P. 2008).

GABA(a) agonists being the most widely used hypnotics could cause residual daytime sedation and safety concerns like the risk of drug addiction, overdose and intoxication along with cognitive toxicity, falls and hip fractures especially in elderly persons (Pagel & Parnes, 2001)

The second approved treatment option for insomnia is cognitive-behavioral treatment of insomnia combining behavioral and psychological techniques. Unlike hypnotics this method has consistent long-term efficacy with few adverse effects (Morin et.al., 2016). On the other hand it requires special training of therapist, compliance of patient and noticeable time expenditures of both. Hence shortened and simplified behavioral approaches have been developed. It includes brief behavioral treatment for insomnia (BBT-I) lasting four weekly sessions instead of 6-8, online sessions, telephone consultations, and self-help approaches. Although there are not enough data for meta-analysis, BBT-I proved its efficacy in a number of clinical comparative studies (Bootzin, 2004).

STUDY RATIONALE

Even after considering all the specific advantages and drawbacks of pharmacological and cognitive-behavioral methods of CI treatment a clinician would be still in question, which one would be preferable in a particular case. There are still questions about the reason why CBT or pharmacotherapy or even their combination didn't reach 100% treatment response. So the treatment response predictors identification is required for individualized treatment

Risk / Benefit Assessment

Brief behavioral therapy has no potential adverse effects, risks of addiction or tolerance.

Zopiclone has possible hypersensitivity adverse effects as well as possible effects on central nervous system: taste disturbance; less commonly nausea, vomiting, dizziness, drowsiness, dry mouth, headache; rarely amnesia, confusion, depression, hallucinations, nightmares; very rarely light headedness, incoordination, paradoxical effects. Nevertheless it remains medication recommended for insomnia treatment in accordance with international guidelines

STUDY OBJECTIVES

Primary Objective

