To test the effectiveness of short BBT-I program for chronic insomnia in comparison with zopiclone in Russian population.

Secondary Objectives

Identification of anthropometric, psychological and polysomnographic predictors of effectiveness of each method.

STUDY DESIGN

Study Overview

Prospective randomized crossover study. In accordance with this design every patient will receive two different treatment courses in random sequence: zopiclone or structured educational program (BBT-I) delivered in two sessions. Patients of the zopiclone-first group will receive the medication therapy for the first two weeks followed by educational program. Patients of the BBT-I-first group will receive two-week educational program followed by medication therapy.

Each treatment course will be separated by 2-weeks washout period that will provide the opportunity to evaluate the sustainability of treatment effect.

The total duration of the study will be 8 weeks with 6 visits including 1 night polysomnography (PSG), 2 face-to-face structured educational program sessions and 5 diagnostic interviews. Total duration of the study will be 2 years.

Criteria for evaluation

Primary Efficacy Endpoint

Proposed primary efficacy endpoint is change of insomnia severity index (ISI) after treatment. Criterion of response to the treatment will be defined as the reduction of ISI score reduction of >7 points from baseline. This criterion is indicative of moderate improvement and validated as clinically significant (Morin, Belleville & Belanger, 2011). Remission criterion will be defined as final

ISI score of 7 points or less. Nonresponse criterion will be defined as ISI score decrease of ≤ 7 points from baseline.

Secondary Efficacy Endpoints

1. Insomnia severity index self reported insomnia symptoms severity . Each item is scored 0 (no problem) - 4 (very big problem) with total between 0-28 (absence of insomnia (0-7); sub-threshold insomnia (8-14); moderate insomnia (15-21); and severe insomnia (22-28).
2. Beck Depression Inventory. 21-item questionnaire assessing (on 4-point Likert scales) the intensity of depressive symptoms in the past week
3. State-trait anxiety inventory. 2-part questionnaire assessing state (situational) and trait anxiety. Both situational and trait parts comprise 20 items rated on a 4-point Likert scale.
4. Dysfunctional beliefs about sleep scale. questionnaire assessing sleep related cognitions in 16 item rated on a 10-point Likert scale.

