All concomitant medication and concurrent therapies will be documented at baseline examination and at visit days. Dose, route, unit frequency of administration, and indication for administration and dates of medication will be captured.

Demographics

Demographic information (date of birth, gender) will be recorded at baseline examination.

Medical History

Relevant medical history, including history of current disease, other insomnia history, and information regarding underlying diseases will be recorded at baseline examination.

Physical Examination

A complete physical and neurological examination will be performed by the investigator who is a neurologist at baseline examination.

Vital Signs

Body temperature, blood pressure, pulse will be measured after resting for 5 minutes at baseline examination.

Polysomnography

1-night in-lab PSG (without adaptation night) will be performed at baseline examination. Standard polysomnography montage includes 6 monopolar electroencephalography (EEG) channels Fp₁A₂, Fp₂A₁, C₃A₂, C₄A₁, O₁A₂, O₂A₁; 1 submental electromyogram (EMG) channel; 2 electrooculogram (EOG) channels; 2 EMG channels of the right and left tibialis anterior muscles; 1 electrocardiogram channel; oronasal airflow pressure; thoracic and abdominal efforts; respiratory sound; oxygen saturation; body position with videomonitoring

Questionnaire

Subjects will be asked to fill in self-report questionnaires: Beck Depression Inventory (BDI), State-trait anxiety inventory (STAI), Toronto Alexithymia Scale – short version TAS-20, Big Five Questionnaire (BFQ-2R), Pittsburg Sleep Quality Index (PSQI), Insomnia Severity Index (ISI), Dysfunctional beliefs about sleep scale (DBAS), Sleep hygiene index (SHI) at baseline examination.

During the next 4 visits participants will repeatedly undergo diagnostic tests including BDI, STAI, PSQI, ISI, DBAS, SHI.

Adverse Events

Information regarding occurrence of adverse events will be captured throughout the study. Duration (start and stop dates and times), severity, outcome, treatment and relation to study drug will be recorded on the case report form (CRF).

Clinical Laboratory Measurements

β -adrenoreactivity test

Peripheral blood sample will be collected in a sterile tube and tested in lab for erythrocyte membranes β -adrenoreactivity by a method based on detection of adrenoreceptor sensitivity to-endogenous catecholamines

EVALUATIONS BY VISIT

Visit 1 (Day 1/Week 1/ Month 1)

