Subjects withdrawn from the study treatment will be replaced. Subjects withdrawn from the study after Visit 5 but prior to Visit 6 won't be replaced.

Protocol Violations

Protocol violations for this study include, but are not limited to, the following:

- Failure to meet inclusion/exclusion criteria

- Use of a prohibited concomitant medication
- Non-compliance with study drug regimen, and questionnaires completion

Failure to comply with Good Clinical Practice (GCP) guidelines will also result in a protocol violation. If a protocol violation occurs, a Protocol Violation Form detailing the violation will be generated.

DATA SAFETY MONITORING

There will be no data monitoring committee

STATISTICAL METHODS AND CONSIDERATIONS

A Statistical Analysis Plan (SAP) is written describing all analyses that will be performed.

Data Sets Analyzed

All subjects matching inclusion and exclusion criteria who will complete at least one treatment course (BBT-I or medication) and fill in questionnaires prior and after the treatment will be included in the safety analysis.

Demographic and Baseline Characteristics

The following demographic variables at screening will be summarized by dose level: gender, age, height and weight. Continuous variables will be presented in means and standard deviation ($M \pm SD$).

Analysis of Primary Endpoint

Statistical significance of differences between ISI level before and after treatment for both treatment methods will be evaluated with Student's t-test after confirmation of normal variable distribution by Kolmogorov-Smirnov test. For continuous variables with distribution other than normal Mann-Whitney U-test will be used. For comparison of the proportions Pearson chi-squared test will be performed.

Criterion of response to the treatment is defined as the reduction of ISI score reduction of >7 points from baseline. This criterion is indicative of moderate improvement and validated as clinically significant (Morin, Belleville & Belanger, 2011). As well the criterion corresponds to approximately 1 standard deviation of the pretreatment values (Cohen effect size of approximately 1.0). Remission criterion is defined as final ISI score of 7 points or less. Nonresponse criterion is defined as ISI score decrease of ≤ 7 points from baseline.

Analysis of Secondary Endpoints

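### Remission is a bare cut on a final ISI with no visit and no starting score, so a remission left over from course 1 can be credited to the second method

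*Combined protocol and SAP*

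**What the plan says.** The synopsis (Primary Analysis Plan) and the section Analysis of Primary Endpoint both state: "Remission criterion is defined as final ISI score of 7 points or less". Criteria for evaluation, Primary Efficacy Endpoint, has the same rule, beginning "Remission criterion will be defined as final". None of the three says which visit supplies the final score, which course it belongs to, or what the score must have been beforehand. The neighbouring response rule is a change score: "Criterion of response to the treatment is defined as the reduction of ISI score reduction of >7 points from baseline".

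The Study Overview says that "every patient will receive two different treatment courses in random sequence", with a "2-weeks washout period that will provide the opportunity to evaluate the sustainability of treatment effect". ISI is taken at baseline, and the Questionnaire section adds: "During the next 4 visits participants will repeatedly undergo diagnostic tests including BDI, STAI, PSQI, ISI, DBAS, SHI". (The questionnaire row in Appendix 1 lists the other scales without ISI; I rely on the Questionnaire section.) Under Evaluations by Visit, course 1 runs from Visit 1 to Visit 2 and course 2 from Visit 3 to Visit 4. Visits 3 and 5 close the two washouts.

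For binary outcomes, Analysis of Primary Endpoint says only: "For comparison of the proportions Pearson chi-squared test will be performed".

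**The concern.** In a two-course crossover, an outcome meant to describe a method must be tied to the course in which that method was given. The remission rule is not. It has no starting score, so it cannot tell a remission reached on a course from one already present when the course began.

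Nothing else in the plan closes the gap. The inclusion criteria set no minimum ISI, and no condition on ISI applies at Visit 3. The washout is itself used to see whether effects last, so the plan allows that some patients will enter course 2 still improved.

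Fixing the baseline for change and response, at Visit 1 or at Visit 3, does not help, because remission uses no baseline. If baseline means course start, the rules can also disagree: a patient who begins course 2 at 7 or less can fall by at most 7 points, so is a nonresponder to that course by rule, yet can be its remission.

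At stake is any statement about how many patients each method brought to remission.

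**Working it through.** The documents give no remission rate, persistence figure or sample size calculation, so there is no figure of the plan's own to reproduce.

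**Step 1. Apply the rule under each reading of the final score.**

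- *End of course (Visit 2 or 4).* Take a BBT-I-first patient with ISI 18, 7, 6, 6, 6 at Visits 1 to 5. The change on zopiclone is 6 − 6 = 0, yet Visit 4 is 7 or less, so zopiclone is credited with a remission.
- *End of washout (Visit 3 or 5).* The same patient has 6 at Visit 5 and is again a zopiclone remission. The start of the course is still ignored.
- *Last study visit (Visit 5).* Each completer has one status, reached after both treatments. If 12 of 40 are at 7 or less, both methods show 12/40 = 30% and the difference is 0 whatever the data.

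**Step 2. Size under the end-of-course reading, with a second method that does nothing.** All inputs are assumptions except the larger SD. Analysis of Primary Endpoint equates a change of more than 7 points with about 1 pretreatment SD, which implies an SD near 7.

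Model: patient mean T; first-course effect e (SD 4); visit noise SD 2; share p of the effect persisting. V1 = T + noise; V3 and V4 = T − p·e + noise, with separate noise at each visit. Scores are rounded and held within 0–28. Result: share with V4 ≤ 7 among patients with V1 > 7. With a between-patient SD of 3.5, the Visit 1 SD is √(3.5² + 2²) ≈ 4.0:

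| Mean ISI, effect | p = 0 | p = 0.5 | p = 0.75 | p = 1 |
|---|---|---|---|---|
| 19, 6 | 0.2% | 2.8% | 8.1% | 16.6% |
| 17, 6 | 0.6% | 6.9% | 15.5% | 26.3% |
| 15, 8 | 2.0% | 19.8% | 36.6% | 52.2% |

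With a Visit 1 SD of about 7, the same three scenarios give 2–4%, 8–21%, 14–33% and 21–45%. Over both SDs the ranges are about 0–4%, 3–21%, 8–37% and 17–52%.

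**Step 3. Direction, by simple counts.** Assume 20 patients per sequence, 40% remission in course 1 on both methods, no effect of either second course, and 80% of BBT-I but 20% of zopiclone remissions persisting.

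- Inherited by zopiclone given second: 20 × 0.4 × 0.8 = 6.4.
- Inherited by BBT-I given second: 20 × 0.4 × 0.2 = 1.6.
- Pooled zopiclone: (8 + 6.4)/40 = 36%. Pooled BBT-I: (8 + 1.6)/40 = 24%.

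Equal course 1 rates become a 12-point difference. With equal persistence on both methods the pooled rates stay equal (at 50% each, (8 + 4)/40 = 30% for both). With no persistence nothing is inherited.

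**Step 4. Effect of requiring a score above 7 at course start.** Among patients with V3 > 7, the rate credited to a second method with no effect falls, at mean 17 and effect 6, to 3.7%, 6.5% and 8.9% for p = 0.5, 0.75 and 1. Across the three scenarios at the smaller SD, the residual with persistence is about 2–17%. It comes from patients near the cut who cross it through visit noise.

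**The case against.** The best reply is that context settles the meaning. Analysis of Primary Endpoint speaks of ISI before and after treatment for each method, and responders are classified per method. A patient with only one completed course can be analysed. The final score is therefore most naturally the end-of-course score. That stands, and it makes the last-visit reading the less likely one. A reader might infer that the plan gives both methods the same remission status by construction; the documents do not support this as the plan's intent. But the end-of-course reading is the one under which remissions are carried into course 2.

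A second reply is that no between-method test of remission is named. The chi-squared sentence is general, and the only stated use of a binary criterion is the responder split for predictors. That also stands: a distorted remission test is something a reader might infer, not something the plan specifies. Still, remission is defined under the primary endpoint, and chi-squared is the planned test for proportions.

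Third, one might infer from the plan that the error must favour zopiclone. Overview of Clinical Studies does say "Unlike hypnotics this method has consistent long-term efficacy with few adverse effects", but of cognitive-behavioural treatment in general. It introduces brief therapy afterwards as a shortened form, without claiming lasting effects for a two-session programme. The direction is therefore conditional.

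Finally, without persistence the error is negligible, and the documents do not quantify persistence.

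**Conclusion.** The point holds in conditional form. As written, the rule lets a remission present at the start of course 2 be counted for the second method, and nothing in the plan prevents it. This is a stated rule that can misattribute outcomes, not merely a missing detail.

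Its size cannot be fixed from the documents. Under the assumptions in the working, it runs from negligible with no persistence to about half of patients at the extreme (mean 15, effect 8, full persistence, smaller SD). If behavioural effects outlast hypnotic effects, the error would favour zopiclone given second; if they persist equally, it inflates both methods.

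The main ISI change comparison does not use this rule. The change should be made, but the trial's principal result does not rest on it.

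**What to change.** In the synopsis, in Primary Efficacy Endpoint and in Analysis of Primary Endpoint, replace the rule with wording such as: remission on a course is an ISI of 7 or less at the end of that course (Visit 2 for course 1, Visit 4 for course 2) in a patient whose ISI at its start (Visit 1 or Visit 3) was above 7. Patients at 7 or less at the start of a course are reported separately as already in remission and are not credited to that method.

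If remission is compared between methods, show the course 1 comparison, where the groups are as randomised. Present course 2 remission descriptively, split by Visit 3 status.

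The scores needed are already planned under the Questionnaire section. The costs are statistical:

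- Fewer patients count in course 2, and they are a selected group who were above 7 at Visit 3.
- The between-method comparison becomes a parallel-group one with about 20 patients per sequence, assuming equal allocation of the 40; the plan gives no ratio.
- Noise crossings remain, as shown in Step 4, so course 2 figures should not be read as clean treatment effects.

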
STATISTICS Primary Analysis Plan
	
Analysis of insomnia treatment will be conducted only for patients matching inclusion and exclusion criteria who will complete at least one treatment course (BBT-I or medication) and fill in questionnaires prior and after the treatment. Continuous variables will be presented in means and standard deviation (M±SD). Categorical and rank variables will be presented as percentages.
 
Statistical significance of differences between group for continuous variables will be evaluated with Student’s t-test after confirmation of normal variable distribution by Kolmogorov-Smirnov test.
 
For continuous variables with distribution other than normal Mann-Whitney U-test will be used. For comparison of the proportions Pearson chi-squared test will be performed.
 
Criterion of response to the treatment is defined as the reduction of ISI score reduction of >7 points from baseline. Remission criterion is defined as final ISI score of 7 points or less. Nonresponse criterion is defined as ISI score decrease of ≤7 points from baseline. Based on these dichotomic values participants will be divided into two groups: responders and nonresponders for each method of treatment.
 
Comparison of responders and nonresponders baseline quantitative characteristics will be performed using Student’s t-test (for normal data distribution) or Mann-Whitney U-test (for abnormal data distribution). Statistical significance will be set at a p-value less 0,05.

Rationale for Number of Subjects
	
Study design allows to compare two therapeutic approaches with a relatively small sample size and to determine the predictors of effectiveness for each treatment. Thus 40 patients get 2 therapeutic approaches. This is the representative sample size enough to produce normal variable distribution for further parameter statistical analysis.

PURPOSE OF THE INVESTIGATION

Name of investigational method

Brief behavioral therapy program
Imovan (zopiclone)

Intended use of the investigational method

2-week Brief behavioral therapy will be performed in two 1 hour session for treatment of chronic insomnia (CI)

Imovan (zopiclone) in a dose of 7,5 mg has to be taken 30 minutes before bedtime for two weeks

Overview of Clinical Studies

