Statistical significance of differences between BDI, STAI, PSQI, DBAS, SHI, β -adrenoreactivity level, sleep diary data before and after treatment for both treatment methods will be evaluated with Student's t-test after confirmation of normal variable distribution by Kolmogorov-Smirnov test. For continuous variables with distribution

other than normal Mann-Whitney U-test will be used. For comparison of the proportions Pearson chi-squared test will be performed.

Based on the response criterion participants will be divided into two groups: responders and nonresponders for each method of treatment. Comparison of responders and nonresponders baseline quantitative characteristics (polysomnographic, antropometric, psychometric) will be performed using Student's t-test (for normal data distribution) or Mann-Whitney U-test (for abnormal data distribution). Statistical significance will be set at a p-value less 0,05.

Safety and tolerability data will be summarized by treatment group. Adverse events will be tabulated by treatment group and include the number of patients for whom the event occurred, the rate of occurrence, and the severity and relationship to study drug.

Interim Analysis

Interim statistical analysis will be performed after 20 patients complete the study protocol.

Sample Size and Randomization

The number of subjects planned to be enrolled is 40. This is a representative sample for study of treatment effects. The crossover design of the study will allow us to compare two therapeutic approaches with a relatively small sample size and to determine the predictors of effectiveness for each treatment.

DATA COLLECTION, RETENTION AND MONITORING

Data Collection Instruments

The Investigator will prepare and maintain adequate and accurate source documents designed to record all observations and other pertinent data for each study subject. The information corresponding to each visit will be entered to the study database and to paper CRF.

The Investigator is responsible for all information collected on subjects enrolled in this study. All data collected during the course of this study will be reviewed and verified for completeness and accuracy by the Investigator.

Data Management Procedures

The data will be entered into a validated database. The Investigator is responsible for data processing, in accordance with procedural documentation.

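### The only predictor analysis replaces continuous ISI change by a responder split at more than 7 points; under a normal model with a mid-range response rate this discards about 36–50% of the information

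*Combined protocol and SAP*

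**What the plan says.** In Study Design (Primary Efficacy Endpoint), ISI is treated as a score: "Proposed primary efficacy endpoint is change of insomnia severity index (ISI) after treatment". The Secondary Efficacy Endpoints list gives its range as 0–28. Analysis of Primary Endpoint tests ISI before and after treatment as a continuous variable and then adds a threshold: "Criterion of response to the treatment is defined as the reduction of ISI score reduction of >7 points from baseline". It supports the threshold as clinically significant and adds: "As well the criterion corresponds to approximately 1 standard deviation of the pretreatment values".

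Predictors are handled in Analysis of Secondary Endpoints: "Based on the response criterion participants will be divided into two groups: responders and nonresponders for each method of treatment". Then: "Comparison of responders and nonresponders baseline quantitative characteristics (polysomnographic, antropometric, psychometric) will be performed using" Student's t-test or, for non-normal data, the Mann-Whitney U-test, at p < 0.05. The synopsis has the same plan: "Based on these dichotomic values participants will be divided into two groups". Neither place plans a regression or correlation with continuous ISI change.

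Under Sample Size and Randomization, "The number of subjects planned to be enrolled is 40". One reason given is that the crossover allows the investigators "to determine the predictors of effectiveness for each treatment". No power, effect size, SD of change or expected response rate accompanies the number.

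**The concern.** The split treats a patient who improves by 7 points like one who gets worse, and treats improvements of 7 and 8 points as opposite results. Some of this loss occurs wherever the line is drawn, so a better cut-off would not remove it.

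The split is the only planned route to the secondary objective, and that objective is part of the stated case for 40 patients. Lower power means that real predictors are more easily missed and that a null result says little. Forty is also a ceiling for each method, because a patient who finishes only one of the two courses still enters the analysis.

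**Working it through.** **Plan's own figure.** There is nothing to reproduce: 40 is given without the quantities that a sample-size formula needs.

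**Inputs from the documents.** n = 40 per method at most; cut at ISI reduction > 7; significance level 0.05 (two-sided assumed); baseline SD of about 7 points, implied by the remark that the threshold is about 1 SD.

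**Inputs that must be assumed.** Response rate p on this criterion, SD of ISI change, and correlation r between predictor and ISI change. The Overview of Clinical Studies cites effectiveness of 64% and 88%, but for sleep quality and not for this criterion.

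**Step 1: information kept.** For a normal outcome cut so that a proportion p respond, with a weak linear association, the efficiency relative to the uncut outcome is

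E(p) = φ(z_p)² / [p(1 − p)], and effective n = 40 × E(p).

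| Response rate | φ(z_p) | E(p) | Loss | Effective n |
|---|---|---|---|---|
| 50% | 0.3989 | 0.1592/0.2500 = 0.637 | 36% | 25.5 |
| 35% | 0.3704 | 0.1372/0.2275 = 0.603 | 40% | 24.1 |
| 64% | 0.3741 | 0.1400/0.2304 = 0.607 | 39% | 24.3 |
| 20% | 0.2800 | 0.0784/0.1600 = 0.490 | 51% | 19.6 |
| 88% | 0.2000 | 0.0400/0.1056 = 0.379 | 62% | 15.2 |

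The formula is symmetric in p and 1 − p. The smallest loss is 36%, at p = 50%, and the loss reaches 50% at p = 20.9% or 79.1%.

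**Step 2: plausible response rates.** Take whole-point scores, so that response means a change above 7.5, and p = 1 − Φ((7.5 − mean)/SD). If the SD of change is 7 (borrowed from the baseline SD) and the mean reduction is 4 to 12 points, p runs from 31% to 74% and the loss is 36–45%. With an SD of change of 5, the loss reaches 53% at a mean reduction of 12.

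**Step 3: power.** Simulation at n = 40 under bivariate normality, comparing a correlation test on continuous change with a t-test of the predictor by responder status:

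| r | Continuous | Split, 50% respond | Split, 35% | Split, 20% |
|---|---|---|---|---|
| 0.3 | 47–48% | 32% | 30% | 26% |
| 0.4 | 73–75% | 54% | 51% | 42% |
| 0.5 | 92% | 75% | 72% | 61% |

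**Step 4: does the gain survive adjustment?** Step 3 uses simple correlation, whereas the proposed analysis adjusts for ISI at the start of the course. Under assumed SDs, the adjusted regression has 73% power against 49% for the split. Under similar assumptions, the unadjusted split gives about 8.5% false positives at a nominal 5% when a predictor with no effect of its own correlates 0.3 with baseline ISI. These figures move with the assumed SDs.

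**Step 5: a model in which the split does well.** Suppose that patients form two latent classes, the predictor differs by 0.9 SD between them, and the SD of change within a class is 3 (all illustrative). With mean drops of 12 and 2, power is 63% for continuous change and 68% for the split; with 11 and 3, 57% and 58%; with 10 and 4, 45% and 44%.

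**The case against.** The strongest reply is that the split answers the stated clinical question. The Study Rationale asks why treatments fall short of full response and calls for predictors of response, and the threshold is fixed in advance with a clinical justification. This stands as a reason to keep the responder comparison. A reader might infer that it should be dropped or reduced to a descriptive table; the documents do not support going that far. The threshold's clinical meaning still does not justify making the split the only outcome for finding predictors.

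The second reply is that the size of the loss depends on the model. This also stands. A reader might infer that the plan certainly throws away a third to a half of its information. The documents give no response rate, SD of change or predictor correlation, so that cannot be stated as fact. Two clearly separate response classes would bring the loss close to nil (step 5), and 88% response would take it to 62% (step 1).

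The third reply concerns the remedy. In period 2, ISI at the start of the course is the Visit 3 value, measured after the first treatment, while PSG and the personality questionnaires are taken only at Visit 1. Adjusting for Visit 3 ISI may absorb part of a predictor's association. The present plan also has a rank test for non-normal data, which a plain linear regression lacks. Both points are right and are met in the fix.

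**Conclusion.** The concern holds in conditional form. The split is the sole planned predictor analysis, although a continuous score is available. Given roughly normal ISI change, a linear predictor relation and a response rate of about 21–79%, the loss is about 36–50%, and for r = 0.4 power falls from about 74% to 42–54% (the lower figure is at 20% response, just outside that range). Under the normal model 36% is a floor, but 50% is not a ceiling. Outside that model the loss can be small or absent.

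A reader might also infer that the main efficacy result is weakened. It is not: the primary before-and-after test keeps the continuous ISI score. The point reaches only the secondary objective, and the change should be made because it is cheap.

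**What to change.** In Analysis of Secondary Endpoints and the synopsis, make the main predictor analysis, for each method, a linear regression of continuous end-of-course ISI on each predictor, adjusted for ISI at the start of that course and for sequence. In addition:

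- Repeat it using period 1 only, or with Visit 1 ISI in place of Visit 3 ISI, as a sensitivity check. Period 1 alone has about 20 patients per method if allocation is equal, and power for r = 0.4 is then about 43% even with the continuous outcome, so read it for consistency and not for significance.
- Use a rank-based version for markedly skewed predictors.
- Keep the responder/nonresponder comparison as a supportive analysis, since more than 7 points is the plan's clinically significant threshold.
- State that power for predictors is limited and depends on a response rate that is not yet known.

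The cost is SAP wording and a little more analysis. No new data are needed: the Questionnaire section has ISI at baseline and at the next four visits. The downside is that a slope is less direct to read than two group means, which the supportive comparison still supplies.
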